3. STUDY DESIGN

This will be a phase 2 multicenter, double blind, placebo controlled randomized clinical trial.

4. STUDY POPULATION

4.1 Population (base)

Comatose patients (GCS score of 8 or lower) after cardiac arrest and successful cardiopulmonary resuscitation, admitted to intensive care units of participating hospitals, will be included within 12 hours after return of spontaneous circulation. Informed consent and randomization will have to be obtained within 12 hours after return of spontaneous circulation. The trial treatment will have to be started within three hours after randomization (please see procedure at 7.3).

4.2 Inclusion criteria

In order to be eligible to participate in this study a subject must meet the following criteria:

- Age ≥ 18 years
- Out of hospital cardiac arrest
- Successful cardiopulmonary resuscitation
- Return of spontaneous circulation ≤ 12 hours ago
- GCS score on admission ≤ 8 or suspected coma in patients who are sedated
- Admission to intensive care unit
- Hemodynamic and respiratory stability as determined by the treating intensive care physician, with the minimum requirement of mean arterial pressure > 65 mmHg. Treatment with inotropes, vasopressors or IABP is allowed.

Of note, cardiac arrhythmia is frequently observed in the patient group under study. Patients with cardiac arrhythmia can be included and with cardiac arrhythmia after inclusion, trial treatment can be continued, unless the treating intensive care physician decides otherwise.

4.3 Exclusion criteria

A potential subject who meets any of the following criteria will be excluded from participation in this study:

- Age < 18 years
- A known progressive neurological disease
- Expected death within 48 hours

4.4 Sample size calculation

This is a phase 2 trial aiming at estimation of safety and potential of efficacy. Power calculations are hampered by lack of any data on ghrelin effects in patients with postanoxic encephalopathy. An intended sample size of 160 patients is based on analysis of any shift in the direction of a better outcome on the CPC scale, a mean CPC score without treatment at six months of 3.20, SD of 1.8 (based on our observations on natural history in 277 patients)⁷, a mean difference between treated and untreated patients of 0.8 points on the CPC scale, alpha of 0.05 and power of 80%. The mean difference of 0.8 points on the CPC scale may be an overestimation of potential benefit. The consequent relatively small sample size is considered justified, given the need for larger future phase 3 trials if potential benefit is demonstrated. Interim analyses will only be directed at safety (comparison of SAEs between treatment groups), so no additional subjects need to be included to compensate for interim analyses.

5. TREATMENT OF SUBJECTS

The trial treatment will consist of intravenous treatment with acylated ghrelin 600micrg dissolved in 50cc normal saline by bolus (short term) infusion in at least 30 minutes twice daily, for 1 week vs. placebo (i.e. 50cc normal saline without ghrelin).¹⁷ Treatment duration of one week is chosen because (i) ill-fated neuronal inactivity is mainly observed in the acute phase (first days) after cardiac arrest and (ii) previous phase 0 and 1 studies have proven safety with a treatment duration of one week.¹⁷

This trial treatment will be additional to current care. This indicates that all patients are treated according to national and local protocols for comatose patients after cardiac arrest. This includes targeted temperature treatment at 36°C in all participating centers.

6. INVESTIGATIONAL PRODUCT

6.1 Name and description of investigational product(s)

Active treatment group: Acyl-ghrelin in normal saline

Placebo group: normal saline

6.2 Summary of findings from non-clinical studies

Hypoxic-ischemic brain damage in vitro: ghrelin treatment was associated with a massive increase of physiological neuronal activity and formation of new synapses in cultured neuronal networks exposed to hypoxia / ischemia.⁹

In vivo rat models of hypoxic ischemic brain damage after cardiac arrest: ghrelin prevented apoptosis in living rats after cardiac arrest, with less irreversible neuronal damage and better neurological recovery.¹⁰

In vivo rat models of hypoxic ischemic brain damage induced otherwise, mainly by intraluminal vessel occlusion: in more than ten rat studies on focal or global cerebral ischemia and reperfusion, ghrelin improved neuronal survival and functional recovery without exception, where in most studies it was assumed that ghrelin prevented apoptosis (For a review please see¹¹)

6.3 Summary of findings from clinical studies

Ghrelin has been administered as an infusion or a bolus in a variety of doses to at least 1850 study participants, including healthy participants and patients with obesity, prior gastrectomy, cancer, pituitary disease, diabetes mellitus, eating disorders, cardiovascular disease and neurodegenerative disease (for reviews please see^{17,18}). In patients with neurological diseases, ghrelin treatment was found to be associated with neuroprotection.¹⁸ In patients with cardiovascular diseases, ghrelin treatment was associated with improved cardiac functioning.¹⁷ Ghrelin has not been administered to comatose patients after cardiac arrest, so far. Taken together: there is strong evidence that ghrelin stimulates appetite and increases circulating GH, ACTH, cortisol, prolactin, and glucose across varied patient populations. There is a paucity of evidence regarding the effects of ghrelin on LH, FSH, TSH, insulin, lipolysis, body composition, cardiac function, pulmonary function, the vasculature, and sleep.

6.4 Summary of known and potential risks and benefits

At the doses evaluated in the 66 published studies with adverse event reporting, ghrelin demonstrated an excellent short-term safety profile with few adverse effects.¹⁷ Serious adverse events such as pneumonia, enteritis, and lung cancer were extremely rare and

difficult to attribute to ghrelin administration. Mild adverse events occurred in approximately 20% of participants receiving ghrelin. The most common effect was transient flushing, which occurred in 10% of volunteers, but resulted in discontinuation of study medication in only 3 of the 939 participants in whom adverse event collection was reported.²⁰⁻²² The most common gastrointestinal side effect was gastric rumbles, which occurred in 22 participants (2.3%) and was never severe enough to lead to ghrelin discontinuation. Few participants developed neurocognitive effects including temporary somnolence, fatigue, vertigo, or change in mood (26 subjects, 2.8%).¹⁷

6.5 Description and justification of route of administration and dosage

Justification of intravenous route: In all preclinical and clinical studies, intravenous administration was used, either as a bolus or as continuous infusion.¹⁷

Justification of bolus infusion (which in this study is not bolus infusion in a narrower sense, but rather short term infusion in at least 30 minutes): We chose for bolus (short term) infusion, because (1) bolus (short term) infusion suits with the natural evolution of endogenous ghrelin concentrations, which fluctuates over time, and (2) in human studies, effects of ghrelin were largest with bolus infusions as compared with continuous infusion.¹⁷ There was no difference in the percentage of participants experiencing relevant adverse events between bolus and infusion routes of administration.¹⁷ However, somnolence and fatigue occurred more often with bolus infusion. Therefore, to minimize the risk of relevant side effects, instead of bolus infusion in a narrower sense, we chose to apply short term infusion in with an infusion rate of max 10 µg/kg/30min, which indicates an infusion time of at least 30 minutes.

Justification of dosage: Starting point for the chosen regimen of 600µg/dose, two times daily, was optimization of the probability of treatment effect. The highest tested and safe dose regimen is 10µg/kg/dose for single doses. The highest tested regimen for treatment during one week or more is 3µg/kg/dose, two times daily, in human studies. In animal studies, intraperitoneal application of 10-200µg/kg/dose, two times daily during 3-8 weeks, was safe. Given these data, and with an elimination half-life of 27 to 31 minutes,²³ we chose for max 10µg/kg/dose, infused in at least 30 minutes. In close deliberation with the collaborating intensive care physicians, we chose a fixed quantity of 600µg/dose for pragmatic reasons. This is equal to approximately 7.5-10µg/kg/dose. Larger ghrelin doses possibly increased the risk of flushing, as indicated by the higher rate of flushing in the 2 ghrelin bolus studies that employed the largest tested dose (10µg/kg).¹⁷ However, there was no association between dosage and serious adverse events.

Justification of treatment duration: We chose for a treatment duration of one week based on our previous studies, from which we know that the most robust changes of brain functioning (either recovery or secondary deterioration) take place in the first week after cardiac arrest. We justify this treatment duration of one week with previous human studies, where numbers of AEs in studies with treatments during 7, 10, or 14 days were equal to those in studies with shorter treatment durations⁹.

6.6 Dosages, dosage modifications and method of administration

Active treatment group:

Acyl ghrelin 600µg in 50cc normal saline, intravenously, twice daily during one week.

The dosage will be modified in patients of less than 60kg to 10µg/kg.

Placebo group:

50cc normal saline

6.7 Preparation and labelling of Investigational Medicinal Product

Preparation and labelling of the investigational product will be done according to the GMP guidelines. Please also see the attached pharmacy manual and label text.

6.8 Drug accountability

Please see Pharmacy Manual.

7. METHODS

7.1 Study parameters/endpoints

7.1.1 Main study parameter/endpoint

The primary outcome measure will be functional outcome as expressed as the score on the cerebral performance category (CPC) at 6 months.

7.1.2 Secondary study parameters/endpoints

Secondary outcomes include case fatality at one week and 6 months, time to awaken (time interval between resuscitation and GCS score of 14), EMV score and estimated CPC score at 1 week, CPC score at 3 and 12 months, and cognitive functioning at 12 months.

Cardiovascular secondary outcome measures are:

Mean arterial blood pressure day 1-7 (mean, highest, lowest)

Heart rate day 1-7 (mean, highest, lowest)

Arrhythmia day 1-7: yes / no. If yes: type of arrhythmia

Cumulative dose of vasopressive medication day 1-7

Cumulative dose of inotropic medication day 1-7

Sequential Organ Failure Assessment score day 1-7

Kidney function day expressed as GFR day 1-7

CVVH day 1-7: yes / no

Assist devices day 1-7: yes / no

Biomarkers are:

Cardiac: troponine and CK / CK-MB ratio at day 0, 1, 2 or 3

Neurological: NSE day 1, 2, 3

Endocrinological: cortisol, growth hormone, prolactine, ACTH, IGF-1 day 1, 2, 3

Highest glucose levels at day 1-7

Gastro-intestinal outcome measure is: gastric residual volume (day 1-7, during ICU admission)

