2. OBJECTIVES

Primary Objective

We aim to measure safety and efficacy of intravenous treatment with acyl-ghrelin to promote cerebral recovery in comatose patients after cardiac arrest. Safety will be monitored throughout hospitalization and during follow-up using all AEs reported, and by interim analyses by an independent DSMB. Efficacy will be measured by the primary outcome measure, i.e. functional recovery as measured by the Cerebral Performance Category (CPC) scale at six months after cardiac arrest.

Secondary Objective(s):

To measure safety and efficacy of ghrelin to modify

1. Case fatality
2. Time to awaken (time interval between resuscitation and Glasgow Coma Scale (GCS) score of 14)
3. Long term outcome: CPC and cognitive functioning at 12 months
4. Cardiovascular measures:

Mean arterial blood pressure day 1-7 (mean, highest, lowest)

Heart rate day 1-7 (mean, highest, lowest)

Arrhythmia day 1-7: yes / no. If yes: type of arrhythmia

Cumulative dose of vasopressive medication day 1-7

Cumulative dose of inotropic medication day 1-7

Sequential Organ Failure Assessment score day 1-7

Kidney function day expressed as GFR day 1-7

CVVH day 1-7: yes / no

Assist devices day 1-7: yes / no

5. Biomarkers

Cardiac: troponine and CK / CK-MB ratio at day 0, 1, 2 or 3

Neurological: NSE day 1, 2, 3

Endocrinological: cortisol, growth hormone, prolactine, ACTH, IGF-1 day 1, 2, 3

Highest glucose levels at day 1-7

6. Gastro-intestinal: gastric residual volume (day 1-7, during ICU admission)

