9.2 Secondary study parameter(s)

With regard to the range of secondary outcome parameters, we will use simple 2x2 tables, two-group t-tests, Mann-Whitney tests, or multivariable linear and logistic regression models, where appropriate. In all analyses, statistical uncertainty will be quantified by means of 95% confidence intervals. Subgroup analyses based on the EEG pattern at 24 hours will be carried out for the following subgroups: (1) suppressed patterns and suppressed patterns with synchronized periodic activity, (2) continuous patterns, and (3) other patterns. This is based on our previous studies on EEG based outcome prediction of comatose patients after cardiac arrest, where the first subgroup represents patterns that are strongly associated with a poor prognosis, the second subgroup with a good prognosis, and the third subgroup with an intermediate prognosis.[refs] Although the size of this study will not allow for precise estimates of treatment effect in subgroups, we will assess heterogeneity of effects, and analyze consistency of effects on secondary outcomes.

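### Time to awaken requires a total GCS of 14, which needs a verbal score of at least 4, so a patient who wakes while intubated is timed late

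*Protocol*

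**What the plan says.** The protocol fixes the event in two places. Section 2 (Objectives) lists it second among the secondary objectives: "Time to awaken (time interval between resuscitation and Glasgow Coma Scale (GCS) score of 14". Section 7.1.2 repeats it: "time to awaken (time interval between resuscitation and GCS score of 14". Neither place says how the verbal item is scored when it cannot be tested, and neither offers a criterion based on eye or motor response.

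The same section lists "EMV score and estimated CPC score at 1 week" as a further outcome, again with no rule for an untestable verbal item.

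On the population, section 4.2 requires "Admission to intensive care unit" and "GCS score on admission ≤ 8 or suspected coma in patients who are sedated". The second criterion makes an allowance for sedated patients at entry. The awakening definition makes no matching allowance.

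Section 9.2 covers the analysis of all secondary outcomes with a general list that includes "two-group t-tests, Mann-Whitney tests, or multivariable linear and logistic regression models, where appropriate".

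**The concern.** The trial's hypothesis is recovery through mild neuronal activation (sections 1 and 7.1.3), and time to awaken is a direct clinical reading of return of consciousness. A total GCS adds eye, motor and verbal items. A threshold near the top of the total therefore cannot be met without speech, and a patient with a tube in place cannot speak. Such a patient may open the eyes and follow commands and still be recorded as not awake.

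For these patients the recorded time depends partly on when the tube is removed. Section 5 says care follows national and local protocols, so that moment may differ between sites for reasons unrelated to cerebral recovery. At stake are the precision of the comparison on this outcome and the meaning of the reported times.

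**Working it through.** **Inputs.** From the protocol: the threshold of 14 (sections 2 and 7.1.2); entry at GCS 8 or lower, or suspected coma under sedation (section 4.2); and for the sample size "a mean difference between treated and untreated patients of 0.8 points on the CPC scale", SD 1.8, "alpha of 0.05 and power of 80" per cent (section 4.4). Assumed: the standard scale (eye E 1–4, motor M 1–6, verbal V 1–5), V scored 1 when the patient is intubated, and two-sided alpha.

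**Step 1: the plan's own figure.** The protocol gives no figure for time to awaken, so the only one to reproduce is the sample size for the primary endpoint.

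n per arm = 2 × (1.96 + 0.842)² × 1.8² / 0.8² = 2 × 7.849 × 5.0625 ≈ 79.5, rounded up to 80, or 160 in total. Power with 80 per arm is 0.803. The figure reproduces and makes no use of time to awaken.

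**Step 2: which combinations give 14.** Listing all 4 × 6 × 5 = 120 combinations leaves three with a total of exactly 14:

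| E | M | V | Total |
|---|---|---|---|
| 4 | 6 | 4 | 14 |
| 4 | 5 | 5 | 14 |
| 3 | 6 | 5 | 14 |

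Reading the rule as 14 or more adds only E4 M6 V5 = 15. The lowest verbal score in the list is 4.

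**Step 3: highest total by verbal score, with E4 and M6.**

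| V | Highest total | Reaches 14? |
|---|---|---|
| 1 (untestable, scored 1) | 11 | No, 3 short |
| 2 | 12 | No |
| 3 (inappropriate words) | 13 | No, 1 short |
| 4 (confused speech) | 14 | Yes |
| 5 (oriented) | 15 | Yes |

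If an untestable verbal item is left out, the highest total is 4 + 6 = 10.

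**Step 4: who is affected.** For a patient who wakes while intubated, the recorded time is late by at least the interval from waking to extubation. For a patient who is off the ventilator and obeys commands with V3 or lower, the event is not recorded while that verbal score lasts. For a patient who regains consciousness at or after extubation and soon speaks at V4, 14 can mark awakening properly. The protocol does not mention intubation, ventilation or extubation, so the share in each group is unknown.

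**Step 5: illustration of the cost in precision.** None of these inputs comes from the protocol: 40 awakeners per arm, exponential awakening times, control median 2 days, hazard ratio 1.6, Mann-Whitney test at two-sided 0.05, and an exponential lag independent of treatment and recovery. Simulated power:

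| Share of patients with a lag | Mean lag 1 day | 2 days | 3 days |
|---|---|---|---|
| None | about 43% | about 43% | about 43% |
| Half | about 38% | about 31% | about 27% |
| All | about 36% | about 28% | about 22% |

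A mean 1-day lag in half of patients costs about 5 points. The fall to about 22% needs a mean 3-day lag in every patient.

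**The case against.** Five arguments can be made for leaving the definition alone.

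- **Intubation is not in the document.** Correct. It is an assumption, although a reasonable one for comatose or sedated ICU patients. It limits what can be said about size. It does not change the arithmetic for any patient who is intubated.
- **A scoring rule may sit elsewhere.** A substituted or imputed verbal score could be set in the SAP or the case report form instructions, which are not at hand, and would remove much of the problem. This stands as a possibility. But the event itself is fixed in the protocol, twice, and read literally it requires V4.
- **The outcome might be read as no more than time to extubation and clear speech.** A reader might infer this, but it goes too far. E4 M6 V4 reaches 14 and V4 is confused speech, so clear speech is not needed. The delay arises only in patients who wake with the tube in place or whose speech stays impaired. Those who are later extubated and then speak at V4 or better are recorded late, not never.
- **The lag may not be pure noise.** If readiness for extubation or return of speech tracks cerebral recovery, the lag itself carries some treatment signal, and the loss of power is smaller than illustrated.
- **GCS 14 is an explicit threshold that asks for more than following commands.** True. Motor score 6 marks an earlier level of recovery, so the two measures answer somewhat different questions. That is a reason to keep both. It is not a reason to let a measure of awakening depend on whether a tube is in place.

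**Conclusion.** The point holds in a limited form. The protocol's rule needs a verbal score of at least 4. If the verbal item is scored 1 during intubation, the highest total is 11, and a patient who regains consciousness while intubated is not counted as awake until after extubation. An extubated patient who obeys commands with V3 or lower (at most 13) is not counted while that persists.

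The size cannot be computed from the protocol, and the power figures are only an illustration under the assumptions labelled above. They should not be read as an estimate of the loss in this trial.

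A reader might also infer a biased treatment comparison. The document does not support that. Allocation is 1:1, stratified by site, with blinded treating physicians (section 7.2), so the expected effect is mainly added noise and longer recorded times, unless the treatment itself changes time on the ventilator or under sedation. This is one secondary outcome among many; the primary CPC analysis and the sample size of 160 are not affected. The change is worth making because the defect is in a stated definition and the remedy is cheap.

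**What to change.** In sections 2 and 7.1.2, define awakening as the first time after resuscitation that the patient obeys commands (GCS motor score 6), whatever the verbal score. Keep time to GCS 14 or more as a supportive measure. Record the 1-week EMV score as separate E, M and V components, with V marked untestable when the patient is intubated.

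The cost is wording in the protocol and the eCRF. Section 7.3 already makes daily neurological examination part of routine ICU care, so no new assessment is needed there. The downside is that the main measure then marks an earlier level of recovery and is less directly comparable with reports that use GCS 14. The supportive measure covers that.

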7.3 Study procedures

All comatose patients after cardiac arrest will be admitted to intensive care units to receive treatment according to guidelines, as described in national and local ICU protocols.

A legal representative or family member of all eligible patients will be informed about the study as soon as possible after admission on the ICU by the ICU staff/research coordinators. Since any beneficial effect of the treatment under study is assumed to be larger with earlier

initiation, randomization and treatment should be initiated within 12 hours after cardiac arrest (ROSC). All participating centers have ample experience with inclusion of patients with acute cardiac arrest or cerebral ischemia in intervention studies.

Patients who are enrolled in this trial will receive intravenous treatment with acylated ghrelin 600micrg twice daily vs. placebo. The duration of the treatment is one week. This treatment duration of one week will be adhered to, both in patients that remain comatose, and in patients that awaken within a week. If patients are transferred from the ICU to a cardiac care unit or general ward within one week, treatment will be continued for a total of one week, as well. Intravenous treatment will be administered through infusion systems that are already in situ in all of these patients. There will be no additional punctures.

Baseline data will be obtained at admission as part of regular patient care and include: clinical data, EEG data, medical history, and use of medication. In addition, a venous blood samples (5cc) will be taken to measure the baseline ghrelin concentration. This sample will be collected during routine blood sampling; there will be no additional punctures.

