After randomization, daily physical, neurological, and additional examinations at the ICU will be part of routine patient care. In addition, there will be blood sampling for measurement of ghrelin concentrations at day 1 and 3, measures of neuronal damage (NSE at day 1-3), measures of cardiac damage (troponine and CK/CK-MB ratio at day 0-3), hormone concentrations (cortisol, growth hormone, prolactine, ACTH, IGF-1 at day 1-3), and highest glucose levels at day 1-7. All blood samples will be collected during routine blood sampling, if possible; preferably, there will be no additional punctures. However, blood sampling for measurement of ghrelin concentrations will be done at 30±15 minutes after treatment with ghrelin or placebo. For these measurements additional blood samples will be taken, if necessary.

Apart from the study treatment and the venous blood sampling, patients will not be subjected to additional procedures during admission.

Surviving patients will be asked informed consent for participation and additional follow-up on long term outcome. Follow up at 3 and 6 months in surviving patients will be done by telephone interview by a trained research nurse three and six months after admission. The nurse will collect CPC scores based on a standard interview. At twelve months, patients will be invited to the nearest hospital or visited at their place of residence for detailed neuropsychological examination (please see F1 testbatterij NPO for details of the test

battery). Separate informed consent will be asked for neuropsychological examination at twelve months.

Table. Overview of study procedures

	Baseline (Day 0)	Day 0-6	Day 1-7	Day 7	3m	6m	12m
Ghrelin/ placebo treatment		X					
Venous blood sampling (largely within current care)	X		X				
CPC scores				X	X	X	
Neuropsychological examination							X

M = months, CPC = Cerebral Performance Category, to be collected by a telephone interview

The total burden in hours for the patient is max 12 hours. This includes multiple transfusions of the study drug, venous blood sampling, and the follow-up procedures at 3, 6 and 12 months.

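### The day 1-7 window for the cardiovascular and glucose outcomes omits day 0, the first dosing day, and the plain yes/no items also count conditions carried over from entry

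*Protocol*

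**What the plan says.** Protocol sections 2 and 7.1.2 give the same list of cardiovascular measures, each on day 1-7: mean arterial pressure, heart rate, arrhythmia, cumulative vasopressor dose, cumulative inotrope dose, SOFA, GFR, CVVH and assist devices. Highest glucose has the same window. The two items most relevant here read "Arrhythmia day 1-7: yes / no. If yes: type of arrhythmia" and "Assist devices day 1-7: yes / no".

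In the section 7.3 table, the row "Ghrelin/ placebo treatment" is marked under day 0-6, and day 0 is the baseline column. Section 4.1 adds: "The trial treatment will have to be started within three hours after randomization".

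On entry, section 4.2 says: "Patients with cardiac arrhythmia can be included and with cardiac arrhythmia after inclusion, trial treatment can be continued". It also says: "Treatment with inotropes, vasopressors or IABP is allowed". It calls arrhythmia a frequent finding in this population but gives no rate.

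**The concern.** Two features of these definitions work against their use as safety measures.

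The first is the window. By the protocol's own day numbering, the first infusion falls before it opens, and day 7, for which the table shows no treatment, falls inside it. The first exposure matters here. Section 6.3 says ghrelin has not been given to comatose patients after cardiac arrest. Section 12.1 reports elimination half-lives between 10 and 31 minutes, lower arterial pressure after a large intravenous bolus in healthy volunteers and after higher and repeated dosing in heart failure, and a study population that may be unusually vulnerable to cardiovascular events. A fall in pressure, a glucose peak or a short arrhythmia linked to the first infusion could come and go within day 0.

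The second is the yes/no form. Nothing in the item limits it to conditions that begin after treatment starts. A patient who enters with an arrhythmia that continues into day 1 counts as a yes in either arm, which pulls the comparison towards no difference. For a safety measure that is the unhelpful direction.

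**Working it through.** **1. The windows side by side**

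| Item | Days | Source |
|---|---|---|
| Trial treatment | 0-6 | Section 7.3, table |
| Cardiovascular outcomes, highest glucose | 1-7 | Sections 2 and 7.1.2 |
| Troponin, CK/CK-MB | 0, 1, 2 or 3 | Section 7.1.2 |
| Continuous EEG | 0-3 | Section 7.1.3 |

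Twice-daily treatment over seven days is 2 × 7 = 14 doses. One or two of them, including the first, fall on day 0. The protocol does use day 0 for the cardiac biomarkers and the EEG, and sections 2 and 7.1.2 agree on day 1-7, so the window does not look like a slip in one place.

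Day 0 is not defined as a calendar day or as a 24-hour period. A patient first treated overnight might be on calendar day 1 by then. The table as printed still puts the first dose on day 0.

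**2. Dilution from carried-over conditions**

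Let q be the share with the condition at entry and still present on day 1, and let p be the rate of new onset among the others. The yes rate in an arm is

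q + (1 - q)p.

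Subtracting the arms gives a risk difference of (1 - q)(p₂ - p₁). With no drug effect p₁ = p₂ and the difference is zero for any q, so the result is attenuation and not bias under no effect.

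**3. Illustrative size**

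The protocol states no sample-size figure for these outcomes. Its only calculation, for CPC in section 4.4 (difference 0.8, SD 1.8, 80% power), reproduces as 80 per arm and 160 in total with a two-sided alpha of 0.05. That supplies n = 80 and nothing else here.

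Assumed, because no rates are given: p₁ = 0.20, p₂ = 0.40, and q from 0 to 50%. With pₐ and p_b the yes rates in the two arms and p̄ their mean,

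power = Φ{[(p_b - pₐ) - 1.96·√(2p̄(1-p̄)/n)] / √[(pₐ(1-pₐ) + p_b(1-p_b))/n]}.

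For q = 20%: pₐ = 0.20 + 0.80 × 0.20 = 0.36 and p_b = 0.20 + 0.80 × 0.40 = 0.52. Power = Φ[(0.16 - 1.96 × 0.0785)/0.0775] = 53%.

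| q | Yes rates | Risk difference | Risk ratio | Power, plain yes/no | Power, new events in all 80 per arm* |
|---|---|---|---|---|---|
| 0% | 20% v 40% | 0.20 | 2.00 | 79% | 79% |
| 10% | 28% v 46% | 0.18 | 1.64 | 66% | 73% |
| 20% | 36% v 52% | 0.16 | 1.44 | 53% | 66% |
| 30% | 44% v 58% | 0.14 | 1.32 | 42% | 59% |
| 50% | 60% v 70% | 0.10 | 1.17 | 26% | 42% |

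*Unadjusted worst case: no patient with the condition at entry has a new or new-type event, so the rates are (1 - q) × 0.20 and (1 - q) × 0.40 and the risk ratio stays 2.0. If those patients have such events at the same rates as the others, the rates return to 20% v 40% and power to 79%.

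**4. Adding the day 0 loss**

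If a share m of new events is confined to day 0, p becomes p(1 - m). At q = 20%:

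- m = 10%: 34.4% v 48.8%, difference 0.144, power about 46%.
- m = 30%: 31.2% v 42.4%, difference 0.112, power 31%.

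The value of m is also an assumption.

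**The case against.** The strongest reply is that safety does not rest on these items. Section 2 says safety is monitored through all reported adverse events and DSMB interim analyses. Section 8.2.2 records adverse events whether or not they are thought related, with no exclusion of day 0. Section 8.5 gives the DSMB unblinded reports and access to individual files for the first ten patients. A reader might infer that first-dose events go unrecorded. The protocol does not support that: such events are due as adverse events, and an arrhythmia that lasts into day 1 is still counted. What remains is narrower. The always-reported list in section 8.2.2 covers flushing, stomach problems, second arrest and death. It does not name arrhythmia, hypotension or high glucose. Adverse-event reporting depends on an observer and does not replace measures collected in the same way in both arms.

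A second reply is that new-onset definitions and baseline adjustment are commonly left to the SAP, and section 9.2 already provides for regression. That is fair for the carried-over conditions. It does not answer the window, which the protocol itself fixes.

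Third, the yes/no item may be recorded daily, and arrhythmia type is recorded. If so, some resolution and new onset would be visible, so it cannot be said that a patient who enters with an arrhythmia is uninformative whatever follows. The protocol does not say whether recording is daily or once for the week.

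Fourth, no section states that a balloon pump counts as an assist device. Section 4.2 names it separately, and the abbreviation list defines only LVAD. The overlap for that outcome is an inference.

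Finally, a reader might conclude that the comparison is biased between arms. Randomisation balances entry conditions on average, so it is not.

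**Conclusion.** The point holds for the structured secondary outcomes. As written, all nine cardiovascular measures and highest glucose omit the first dosing day, and a transient effect that resolves on day 0 reaches the data only through adverse-event reporting. For arrhythmia, and for assist devices if balloon pumps are included, carried-over conditions shrink any difference by exactly (1 - q).

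The factor (1 - q) is arithmetic; its size in this trial is not known. The protocol gives no rate of arrhythmia at entry, of new onset, or of events confined to day 0, so the power figures illustrate direction and possible scale only. At q = 10% the loss is modest (79% to 66%); it becomes large only if carried-over arrhythmia is common. The primary CPC analysis is not affected, nor is safety monitoring through adverse events and the DSMB. The change is worth making because it costs little and these outcomes are the protocol's planned between-arm comparison of cardiovascular effects.

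**What to change.** Define the window for all the day 1-7 cardiovascular outcomes and for highest glucose as running from the start of the first trial infusion (day 0) to the end of day 7. State what day 0 means by the clock.

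Record whether arrhythmia (with type), an assist device or CVVH is present before the first infusion, and state whether a balloon pump counts as an assist device. Count events that are new, or of a new type, after the first infusion in all randomised patients. Report baseline presence by arm and adjust for it. This is preferable to restricting the analysis to patients free of the condition at entry, which would drop those who enter with one arrhythmia and develop another.

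The cost is protocol and eCRF wording and a little more data entry; the day 0 values are routine ICU data. The new window adds a part-day on day 0 whose length varies between patients, so cumulative doses and means should be expressed per unit of observed time.
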